## 8.4 Adverse events

Adverse events (not SAEs) that are specifically of interest to the trial and that are not bleeding episodes (section 8.2) will be reported on a separate form. These are restricted to:

1. Necrotising enterocolitis  $\geq$  Stage 2 defined as per Bells Criteria (Bell et al, 1978) See below for definitions:

**NEC Definitions:** Only record if category 2 or 3 applies.

### Modified Bell's Staging Criteria for Necrotizing Enterocolitis

STAGE	SYSTEM SIGNS	INTESTINAL SIGNS	RADIOLOGIC SIGNS	TREATMENT
II. Definite				
A: Mildly ill	Same as IA	Same as I, plus absent bowel sounds, abdominal tenderness	Ileus, pneumatosis intestinalis	NPO, antibiotics x 7 to 10 days
B: Moderately ill	Same as I, plus mild metabolic acidosis, mild thrombocytopenia	Same as I, Plus absent bowel sounds, definite abdominal tenderness, abdominal cellulitis, right lower quadrant mass	Same as IIA, plus portal vein gas, with or without ascites	NPO, antibiotics x14
III Advanced				
A Severely ill, bowel intact	Same as IIB, plus hypotension, bradycardia, respiratory acidosis, metabolic acidosis, disseminated intravascular coagulation, neutropenia	Same as I and II, plus signs of generalised peritonitis, marked tenderness and distension of abdomen.	Same as IIB, plus definite ascites	NPO, antibiotics x 14 days, fluid resuscitation, inotropic support, ventilator therapy, paracentesis
B Severely ill: bowel perforated	Same as IIA	Same as IIA	Same as IIB, plus pneumoperitoneum	Same as IIA, plus surgery

2. Sepsis, which must be concurrent. Sepsis is defined for the purposes of this study as culture positive sepsis or culture negative sepsis where a course of at least 5 days of antibiotics is to be administered for proven or clinically-suspected sepsis.

Any adverse event meeting the criteria for seriousness will be reported as an SAE. A listing of adverse events (necrotising enterocolitis, sepsis) will be reported six monthly to the Data Monitoring Committee (DMC).

## 9 OUTCOMES & STATISTICAL CONSIDERATIONS

### 9.1 Randomisation

A web-based randomisation service provided by (<http://www.sealedenvelope.com>) accessible by each participating centre will allocate neonates using minimisation with a random element.

### 9.2 Outcome measures

#### 9.2.1 Primary outcome

The primary outcome measure is the proportion of patients who either die or develop a major or severe bleed up to and including study day 28.

This composite outcome was chosen because these endpoints represent significant clinical outcomes of relevance to the trial question.

Observation up to and including Study Day 28 was chosen for several reasons. First, in the PlaNet-1 study all major bleeds occurred within the 28 days following onset of thrombocytopenia. Secondly, primary outcome measures in many studies in this patient population are measured at Study Day 28.

### **In cases where no imaging is performed within -5 / + 10 days of SD28:**

- If a baby is discharged home well and not readmitted prior to SD28, we will assume no MB had occurred by SD28.
- For babies discharged home after SD28, we will assume that no new major cranial bleed had taken place by SD28 if other Cranial Ultrasound (CUSS), CT or MRI scans performed on or between SD14 and discharge showed no new major bleeding providing that there was no documented episode of any significant clinical deterioration (e.g proven sepsis, NEC, or collapse) that required transfusion with blood products, or evidence of other new major bleeding in that period.
- In cases where no subsequent pre-discharge CUSS, CT or MRI scan was undertaken, providing that there is, prior to discharge, no documented episode of any significant clinical deterioration (e.g. proven sepsis, NEC, or collapse) that required transfusion with blood products, or evidence of other new major bleeding, then we will also assume that there was no major bleed at SD28.
- All other cases are to be dealt with on a case by case basis
- Review of evidence in the first case by [name], Joint Chief Investigator. Further review to be undertaken by medical experts within TMG.
- For difficult cases it may be necessary to refer to an independent neonatologist to review.

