## **2.2 Justification for platelet count thresholds in this randomised trial**

The justification for selection of lower and higher platelet count thresholds at  $25 \times 10^9/L$  and  $50 \times 10^9/L$  for this trial is based on:

1. Current national guidance (BCSH 2004 Handbook of Transfusion Medicine, 2007) recommends platelet transfusion thresholds of  $20-30 \times 10^9/L$  and  $50 \times 10^9/L$  for neonates depending on the clinical situation.
2. In a UK survey, the most common stated thresholds for transfusion were 25 and  $30 \times 10^9/L$  in well infants at term and preterm, respectively (Chaudhary et al, 2009).
3. In PlaNet-1 most transfusions were given at platelet counts between 10 and  $50 \times 10^9/L$  (see histogram below). The 50th and 90th centile pre-transfusion platelet count thresholds observed in the PlaNeT-1 study were 27 and  $48 \times 10^9/L$ .
4. In PlaNeT-1, 173 /415 (42%) transfusions were administered at a minimum platelet count of  $<25 \times 10^9 /L$ , and 383/415 (92%) transfusions were administered at a minimum platelet count of  $<50 \times 10^9/L$ , so there should be clear difference in the intervention between the two arms of this proposed trial
5. The recognition that in the only randomised controlled trial to assess a threshold level for the effectiveness of neonatal prophylactic platelet transfusions, the lower platelet count threshold was  $50 \times 10^9/L$  (Andrew et al, 1993).

The figure below shows the variation of platelet count threshold used for transfusion in the PlaNeT-1 study. This was an observational study and decision to administer a platelet transfusion was at the discretion of the attending clinician.

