### 9.3 Sample size

This trial (PlaNeT-2) represents the first trial in the field of neonatal platelet transfusion prophylaxis in this population of preterm neonates. This study has been designed as a two stage trial with an interim analysis which will inform the final sample size requirement and trial feasibility (See Section 9.4). Data on the frequency of bleeding outcomes in severely thrombocytopenic neonates is available from the PlaNeT-1 survey (Stanworth et al, 2009), in which 30/169 or 18% of neonates died or experienced a major bleed while on study. However, this proportion applies to neonates of all gestational ages, and only during episodes of significant thrombocytopenia. Overall mortality (and new major bleeds) is likely to be greater than this figure derived from PlaNeT-1 data for the baseline event rate in the arm A of this trial. Assuming a proportion of 20% for the primary outcome for Arm A, in order to detect a difference between proportions of 8% (assuming that the proportion in Arm B is 12%), using a two-sided test, 5% significance level and 80% power, 329 neonates in each group is needed. Rounding this figure up, a total of 660 neonates will be required for this study. Note that this calculation does not take account of withdrawals or loss to follow-up.

The Data Monitoring Committee (DMC) will be closely monitoring the primary outcome (mortality and major bleeds) as well as safety data for any imbalance between the two arms (See Sections 10, 11 for further details).

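### For babies with no scan near Study Day 28, the rule that assumes no major bleed turns on blood-product transfusion, which the allocated arm partly drives, so the route of ascertainment can differ by arm

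*Protocol*

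**What the plan says.** The rule is the list in Protocol section 9.2.1 for babies with no imaging in the Study Day 28 window.

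- **Bullet 1:** babies discharged home well and not readmitted before Study Day 28 are taken as having no major bleed. Transfusion plays no part.
- **Bullet 2:** for babies discharged after Study Day 28, no new major cranial bleed is assumed if other scans from Study Day 14 to discharge were clear, there was "no documented episode of any significant clinical deterioration (e.g proven sepsis, NEC, or collapse) that required transfusion with blood products", and there was no evidence of other new major bleeding.
- **Bullet 3:** where there was no later pre-discharge scan at all, the same two clinical conditions suffice.
- **Everything else** is decided case by case. A joint chief investigator looks first, then: "Further review to be undertaken by medical experts within TMG". An independent neonatologist may be asked about difficult cases.

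Sections 6.2 and 6.3 set the randomised contrast: prophylactic platelets below 25 x10^9/L in Arm A and below 50 x10^9/L in Arm B, with discretionary exceptions in both arms for moderate or worse bleeding and for invasive procedures or major surgery. Section 6.6 leaves red cells, plasma and other products to local guidelines. Section 2.2 expects transfusion to differ clearly between the arms and cites PlaNeT-1 in support: "383/415 (92%) transfusions were administered at a minimum platelet count of" <50 x10^9/L, against 173/415 (42%) at <25 x10^9/L.

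**The concern.** Receipt of a blood product is a post-randomisation event, and for platelets it is the event that the arms are designed to make different. Take two babies without a window scan, each with proven sepsis and a count of 35 x10^9/L, and neither given red cells or plasma. The Arm B baby receives platelets under the allocated threshold. If that counts as a deterioration requiring a blood product, the assumption of no bleed fails and the case is reviewed. The Arm A baby generally receives none and is assumed bleed-free. An unseen major bleed can be found in the first baby but not in the second.

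Intention-to-treat analysis and covariate adjustment do not repair this, because the outcome itself would be ascertained unequally. Masking the review would not be enough either, since selection for review already depends on arm. Masking still matters. Section 5.2 makes allocation known to the treating consultant, and the platelet counts and transfusions in a case file could reveal the arm. The wording in section 8.2 about not disclosing allocation covers only the major bleed form.

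**Working it through.** **1. The plan's own sample size.** Section 9.3 states: "Assuming a proportion of 20% for the primary outcome for Arm A", with 12% in Arm B, and "using a two-sided test, 5% significance level and 80% power, 329 neonates in each group is needed". The pooled-variance normal approximation without continuity correction is

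n = [1.960·√(2·p̄·(1−p̄)) + 0.842·√(pA(1−pA) + pB(1−pB))]² / (pA−pB)², with p̄ = 0.16.

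This gives (1.960·√0.2688 + 0.842·√0.2656)² / 0.0064 ≈ 328.5, so 329 per group. The stated figure is reproduced. Section 9.3 rounds up: "a total of 660 neonates will be required for this study". At 330 per arm, power is 80.2%.

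**2. The arm-specific band.** From section 2.2, 383 − 173 = 210, and 210/415 = 50.6% of PlaNeT-1 transfusions were given at minimum counts of 25-49 x10^9/L. Only Arm B transfuses prophylactically in that band.

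**3. Illustrative size.** The protocol gives none of the following, so all are assumptions:

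- m, share of babies without a window scan who fall under bullets 2 and 3: 2-20%
- d, share of these with a significant deterioration: 30-50%
- probability that a deteriorating baby is transfused: 41.7% (173/415) in Arm A and 92.3% (383/415) in Arm B, borrowed from PlaNeT-1
- q, share with an unseen major bleed among those assumed bleed-free: 5-20%
- review finds every bleed

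Babies sent to review per arm = 330·m·d·P(transfused). Bleeds missed per baby randomised = m·d·(1 − P(transfused))·q. The difference between arms is m·d·0.506·q.

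| Case | m, d, q | To review, A vs B | Distortion (points) | Observed difference | Power at 330 per arm |
|---|---|---|---|---|---|
| Low | 2%, 30%, 5% | 0.8 vs 1.8 | 0.015 | 7.98 | 80.1% |
| Middle | 10%, 50%, 10% | 6.9 vs 15.2 | 0.25 | 7.75 | 77.9% |
| High | 20%, 50%, 20% | 13.8 vs 30.5 | 1.01 | 6.99 | 70.3% |

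For the middle case: 0.10 × 0.50 × 0.506 × 0.10 = 0.00253, or 0.25 points, which is 330 × 0.00253 ≈ 0.8 of a baby. The high case is 330 × 0.0101 ≈ 3.3 babies.

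If both true rates were 20%, the nominal 5% two-sided error would be 5.1% in the middle case and 6.2% in the high case.

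**4. Limits of the borrowed shares.** The 50.6% is a share of transfusions, not of babies or of deteriorations, and every PlaNeT-1 transfusion in it was by definition given. The model also ignores red cells and plasma. If a fraction r of these babies would receive another product anyway, they go to review in both arms and the distortion shrinks by the factor (1 − r).

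**The case against.** **The trigger is narrower than transfusion alone.** A documented significant deterioration must have required the transfusion. A routine prophylactic transfusion in a stable baby does not qualify, and it can be argued that platelets given only because a count crossed the allocated threshold do not qualify either. This stands as a limit on scope. The text does not settle it, though, and a septic Arm B baby given platelets fits the wording readily.

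**Other safeguards exist.** Bullet 2 requires clear scans from Study Day 14. Evidence of other new major bleeding sends a case to review on its own in either arm. Scans are due weekly to Study Day 28 and again before discharge for babies who stay longer (section 7.11). Bleeding is also recorded on daily forms and then weekly ones. This stands too: the exposed group may be small, and the point matters most in bullet 3, where no later scan exists.

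**The direction is not fixed.** Arm A babies are transfused below 25 x10^9/L and may be transfused therapeutically above it, and those transfusions also lead to review.

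**Two stronger readings are tempting.** A reader might infer that the rule codes transfused Arm B babies as events. It does not; failing the condition leads to review. A reader might also infer that Arm B's event rate is inflated by 0.5 to 1.5 points, taking 10-20% without a scan, 20-30% of those deteriorating, half transfused only because of Arm B's threshold, and half of those called bleeds. For example, 0.20 × 0.30 × 0.5 × 0.5 = 1.5%. None of these inputs has a source. Half called bleeds is hard to square with the 13% major haemorrhage rate that section 2.1 reports for PlaNeT-1. With 5-20% in its place, the same chain gives 0.05 to 0.6 points. A bleed correctly found in Arm B is also not an error; the error is the one missed in Arm A.

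**Some remedies belong elsewhere.** Counts by arm and sensitivity analyses are commonly left to the statistical analysis plan, so their absence here is not part of this point.

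**Conclusion.** The point holds in a limited form. As written, bullets 2 and 3 let a variable that allocation partly drives decide whether a baby is assumed bleed-free or reviewed. The affected babies are those with no window scan who had a significant deterioration and received platelets but no other blood product.

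The likely direction is fewer bleeds found in Arm A, which would shrink an apparent benefit of the higher threshold, but therapeutic transfusion in Arm A could offset this. The illustrative distortion is about 0.02 to 1.0 points, about 0.25 in the middle case, against 8 points. It rests on unsourced values of m, d and q, on borrowed PlaNeT-1 shares and on perfect review.

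The documents do not show that the reviewers know the arm; they only fail to say that they are masked. Nor do they support a claim that the primary result would be overturned. The defect is systematic, however, and recruiting more babies would not remove it. It should be fixed.

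**What to change.** In bullets 2 and 3 of the list in section 9.2.1, either delete the words that tie the deterioration to transfusion with blood products, or reword them so that platelet transfusion does not count towards the condition. Either change stops allocated platelet transfusion from deciding which babies are reviewed. In the same section, require everyone who reviews these cases, including any independent neonatologist, to be masked to allocation, platelet counts and platelet transfusions. Make both changes before anyone sees outcomes by arm.

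The cost is more case reviews in both arms if the qualifier is deleted, since every qualifying sepsis, NEC or collapse without a window scan would then be reviewed. There would be fewer if only platelets are excluded. Redacted review files must also be prepared. Treatment, visits and the sample size of 660 are unchanged.

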### **9.2.2 Secondary outcomes**

Secondary outcomes include:

- Proportion of patients surviving to go home following a major bleed, censoring at discharge
- Proportion of patients surviving to go home without having had a major bleed, censoring at discharge
- Proportion of patients who have died up to study day 28
- Proportion of patients who sustain a major bleed up to study day 28
- The rate and time from randomisation of minor, moderate and major bleeding derived from the bleeding assessment tool up to study day 14, and for major bleeds up to study day 28. Definitions for all grades of bleeds are shown in the bleeding assessment tool; grading will be assigned based on a modified version of the WHO Bleeding Score
- Number of platelet units transfused up to study day 28
- Time to discharge home, censoring on death
- Neuro-developmental outcome as assessed by the Thames Regional Perinatal Outcome Group/ Standard Electronic Neonatal Database/ National Neonatal Audit Programme (TRPG/SEND/NNAP) 2- year corrected age outcome form at 2 years corrected postnatal age. This will provide a basis of correlation with the WHO functional disability score.
- Platelet transfusion-related adverse events from the time of randomisation up to end of study (section 7.6 and 8.3.2)

A comprehensive statistical analysis plan will be written before the final data analysis is conducted. Analysis of all outcomes will be conducted on the basis of intention to treat. The primary analysis will be adjusted for the stratifying variables.

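### Time to discharge home is defined with deaths censored; death is a competing event, so the discharge curve overstates how many babies go home and hides any mortality difference

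*Protocol*

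**What the plan says.** The list of secondary outcomes in Protocol section 9.2.2 contains "Time to discharge home, censoring on death", and section 1.2 has the same line. Section 9.2.2 promises a statistical analysis plan, which was not available for this review, but the protocol itself already fixes how deaths are handled for this outcome.

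Death is expected in this population. Section 9.2.1, with a 28-day horizon, states: "The primary outcome measure is the proportion of patients who either die or develop a major or severe bleed up to and including study day". Section 9.3 plans on a composite rate of 20% in Arm A and 12% in Arm B.

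Four other provisions bear on the point:
- Section 9.2.2 lists death up to study day 28 as its own secondary outcome.
- It also lists the proportions surviving to go home with and without a major bleed.
- Section 7.10 ends data collection at death, discharge home, 38 weeks corrected gestational age (CGA), or study day 28 if that is later.
- Section 7.13 records all-cause mortality and length of hospital stay.

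Nowhere does the protocol treat death as a competing event for discharge, or limit the outcome to a cause-specific hazard.

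**The concern.** Censoring is harmless when the censored baby would later have had the event at the same rate as those still under observation. Death does not meet that condition, because it rules out discharge for good. A Kaplan-Meier estimate with deaths censored redistributes each dead baby's weight to the babies still in hospital. It therefore describes discharge in a population where nobody dies.

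Two consequences follow:
- **Masking.** The estimated proportion home is too high in both arms, and by more in the arm with more deaths. A real deficit in babies getting home can vanish.
- **Selection.** If the babies who die are those who would have stayed longest, the survivors in the higher-mortality arm are a more favourable group, and that arm can appear to discharge sooner.

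At stake is the reading of one secondary outcome in a trial where mortality may differ between arms.

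**Working it through.** **1. The protocol's own figure.** No figure is given for time to discharge. The only planning figure is the sample size in section 9.3, which starts from "30/169 or 18% of neonates died or experienced a major bleed while on study" and states "Assuming a proportion of 20% for the primary outcome for Arm A", "assuming that the proportion in Arm B is 12" per cent, "using a two-sided test, 5% significance level and 80% power", hence "329 neonates in each group is needed". With the pooled two-proportion formula:

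n = [1.960 × √(2 × 0.16 × 0.84) + 0.842 × √(0.20 × 0.80 + 0.12 × 0.88)]² / 0.08²
= (1.016 + 0.434)² / 0.0064 = 328.5, so 329 per group.

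The figure reproduces. It does not bear on the handling of deaths, but the inputs show that the 20% and 12% are rates of death or major bleed, not of death alone.

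**2. What the protocol offers on deaths.** There is no mortality-only planning rate by arm. The retrospective study described in section 2.1 reports that 22 of 27 transfused babies survived to discharge, so 5/27 = 19% did not. Even if none of the 26 untransfused babies died, that is 5/53 = 9%. This only shows that death rates of the order assumed below are not far-fetched.

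**3. Simulation; all inputs are assumptions.** There are 40,000 babies per arm and the discharge process is identical in both. Severity u is standard normal. Time to discharge in the absence of death is 60 × exp(0.35u + 0.25e) days, with e standard normal, so its median is 60 days. The log-odds of death are a + s·u, with a set to give the target death rate. Time to death is exponential with mean 14 days. Only the death rate differs between arms. Follow-up is not cut off.

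Results for 10% v 20% deaths (lower-mortality arm first; hazard ratio, HR, is higher-mortality over lower-mortality arm):

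| Link of death to severity | Home by day 60, deaths censored | Actually home by day 60 | Median days, deaths censored | Median days, deaths never discharged | HR, deaths censored | Subdistribution HR |
|---|---|---|---|---|---|---|
| None (s = 0) | 50.4% v 50.1% | 45.7% v 40.7% | 59.8 v 59.9 | 63.2 v 68.0 | 1.02 | 0.78 |
| s = 1 | 52.2% v 55.4% | 47.1% v 44.8% | 58.7 v 56.7 | 62.1 v 64.2 | 1.10 | 0.82 |
| s = 2 | 54.1% v 57.4% | 49.0% v 46.4% | 57.5 v 55.7 | 60.7 v 62.7 | 1.07 | 0.80 |

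**4. Hand check of the first row.** Half of the babies would be home by day 60 if none died, and nearly all deaths come before discharge. The proportion actually home is therefore about 0.5 × 0.90 = 45% v 0.5 × 0.80 = 40%, close to the simulated 45.7% v 40.7%. The censored estimate returns about 50% in both arms, so a true deficit of 45.7 − 40.7 = 5.0 points disappears.

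**5. Range.** Over deaths from 5% v 10% to 12% v 20%, with s = 1 or 2, the censored median is 0.6 to 2.0 days shorter in the higher-mortality arm. The censored HR is 1.02 to 1.11 and the subdistribution HR 0.80 to 0.90. The HRs come from 5,000 babies per arm. With about 4,500 + 4,000 = 8,500 discharges, the simulation error on the log scale is about √(4/8,500) = 0.02, so 1.02 cannot be told apart from 1.

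**6. Size against the trial's precision.** With 330 per arm and 10% v 20% deaths there are about 297 + 264 = 561 discharges. The standard error of the log HR is √(1/297 + 1/264) = 0.085. A spurious HR of 1.10 is ln(1.10)/0.085 = 0.095/0.085, about 1.1 standard errors.

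**The case against.** **Censoring at death is a legitimate construction.** It is how a cause-specific discharge hazard is estimated, and the protocol names no Kaplan-Meier curve, median or Cox model. That stands for a hazard ratio labelled as cause-specific and read beside mortality. But the protocol does not limit the outcome to that use, and an outcome called time to discharge will naturally be shown as a curve or a median.

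**Mortality is reported elsewhere.** Death is in the primary outcome and is a secondary outcome to study day 28, and the two survival-to-home proportions could be added to give the proportion discharged alive. This softens the problem. However, the separate death outcome stops at day 28 while discharge is followed to 38 weeks CGA. The survival-to-home outcomes carry no timing and are split by major bleed. None of them corrects the discharge curve.

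**The reversal is small and conditional.** This is right. It needs deaths concentrated among babies with long expected stays, and step 6 shows that it is unlikely by itself to produce a false significant advantage.

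Four stronger readings are tempting, and the documents do not support them:
- That mortality will be 12% v 20%. Those are composite rates; the share due to death is not given.
- That the censored curve would be seen to climb to nearly 100%. Data collection stops at 38 weeks CGA (or study day 28 if later), and section 1.3 puts the latest end of study for the last baby randomised at 31.03.2018, 90 days after 31.12.2017. Even day 60 falls before 38 weeks CGA only for babies randomised before about 29 weeks 3 days (266 − 60 = 206 days).
- That the same fault affects time to bleeding. No censoring rule is stated for that outcome.
- That a subdistribution model is the only remedy. It mixes mortality with length of stay and is one acceptable choice among several.

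**Conclusion.** The point holds for this secondary outcome. The rule is fixed in two places in the protocol, and applied to a discharge curve or median it overstates the proportion going home and hides a mortality difference. With assumed deaths of 10% v 20% it erases a 5-point deficit at day 60 when death is unrelated to severity. When sicker babies die more often, it shows the higher-mortality arm 3.2 points ahead (55.4 − 52.2) although it is 2.3 points behind (47.1 − 44.8).

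Masking needs only that deaths differ between arms; the change of direction also needs the link with severity, which is plausible here but not quantified in the protocol. The death rates, the 60-day median, the time to death and the severity link are all assumed, and follow-up in the simulation is not cut off at 38 weeks CGA. The figures illustrate the mechanism and do not forecast this trial's results. The primary conclusion is unaffected.

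**What to change.** In sections 1.2 and 9.2.2, replace the line with: time to discharge home alive, with death as a competing event. Then specify:
- Show the cumulative incidence of discharge home and of death by arm, side by side.
- Censor babies still in hospital at End of Study at that time; do not censor at death.
- Label any hazard ratio that censors deaths as cause-specific, and report it next to the cause-specific hazard ratio for death.
- A subdistribution model, or counting babies who die as never discharged, is an acceptable alternative.

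The cost is two lines of protocol text and matching wording in the analysis plan. Section 7.13 already provides for recording deaths and length of stay, so no new data and no change to the sample size are needed.

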### **7.12 Two year neuro-developmental follow-up.**

[figure not shown]
Neuro-developmental follow-up will be undertaken by validated Thames Regional Perinatal Outcome Group/ Standard Electronic Neonatal Database/ National Neonatal Audit Programme (TRPG/SEND/NNAP) 2- year corrected age outcome form and will be administered at 2 years of corrected gestational age. The results of the WHO functional disability criteria and any disability will be classified into 3 groups: mild, moderate and severe. A record of all deaths within 2 years after randomisation will be kept.

In order to obtain the 2 year follow-up data, permission will be sought to contact parents at around 2 years CGA when obtaining informed consent for the trial.

Approximately 7 – 10 days before the baby reaches 2 years corrected age a 2 year follow up questionnaire will be posted out by the site research team to the parents/guardians with a self-addressed envelope for completion. The questionnaire is the (PARCA-R) standardised assessment with additional questions adapted from the TRPG survey to obtain information regarding gross and fine motor skills. Permission to contact is outlined in the Informed Consent Form (V3.0). Further contact will be made by the Two year follow up co-ordinator if required, by telephone, email, or text if the questionnaire is not returned. A telephone interview will be offered at this time, or a weblink sent by text or email to complete the questionnaire online if preferred. The process is outlined in Fig 3

Where primary outcome and 2 year follow-up data cannot be obtained by direct contact with parents or clinicians, it may be possible to extract pseudo-anonymised information from the national neonatal database. The research team at the recruiting centre will be able to access this data.

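### The two-year neuro-developmental outcome is defined only for living children, and the deaths recorded to two years have no place in it

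*Protocol*

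**What the plan says.** Protocol sections 1.2 and 9.2.2 list the neuro-developmental secondary outcome by its instrument and time point: "2- year corrected age outcome form at 2 years corrected postnatal age. This will provide a basis of correlation with the WHO functional disability score". Section 7.12 adds a parent questionnaire for the same age and says that "any disability will be classified into 3 groups: mild, moderate and severe". The next sentence there reads "A record of all deaths within 2 years after randomisation will be kept". No section combines those deaths with disability, ranks them against it, or says which infants form the denominator.

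The primary outcome in section 9.2.1 is the "proportion of patients who either die or develop a major or severe bleed up to and including study day 28". The only secondary outcome that counts deaths as such stops at study day 28. Two others count babies surviving to go home, with and without a major bleed. Death is dealt with explicitly for one other item in the same list: "Time to discharge home, censoring on death". Section 9.2.2 closes with "Analysis of all outcomes will be conducted on the basis of intention to treat" and defers detail to a statistical analysis plan, which is not at hand.

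**The concern.** A form, a questionnaire and a disability grade all need a living child. As named, the outcome has no value for an infant who has died, and a death after discharge but before two years enters no listed outcome at all.

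The trial is designed to change a composite that includes death. If the policies differ in mortality, the two sets of survivors are no longer the groups that randomisation created. Babies who live under one policy but would have died under the other are plausibly sicker than average and more often impaired. Comparing disability among survivors then counts their impairment against the policy that kept them alive and gives no credit for their survival. What is at stake is the direction of the trial's only long-term evidence on child development.

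**Working it through.** **The plan's own figure.** Section 9.3 assumes 20% against 12%, two-sided 5%, 80% power. With pooled variance under the null (mean proportion 0.16):

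n = [1.96·√(2·0.16·0.84) + 0.8416·√(0.20·0.80 + 0.12·0.88)]² / 0.08² = (1.016 + 0.434)² / 0.0064 = 328.5, so 329 per arm, or 658, rounded up to 660. This reproduces and is not in dispute. I use 330 per arm below.

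**Inputs for the illustration.** The protocol gives no mortality share and no two-year disability rate, so all of these are assumptions:

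- 15% dead by two years in Arm A, so 85% survive.
- 25% moderate/severe disability among babies who would survive in either arm, the same under both policies.
- Arm B saves a further s = 3, 5 or 8 points.
- A proportion q = 50% or 75% of those extra survivors are impaired.

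**Formulas.**

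- Survivors-only rate in A = 25%.
- Survivors-only rate in B = (0.85·0.25 + s·q) / (0.85 + s).
- Death or disability in A = 0.15 + 0.85·0.25 = 36.25%.
- Death or disability in B = (0.15 − s) + 0.85·0.25 + s·q = 36.25% − s(1 − q).

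| s (points) | q | Survivors only, B | B minus A | Death or disability, B | B minus A |
|---|---|---|---|---|---|
| 3 | 50% | 0.2275/0.88 = 25.9% | +0.9 | 34.75% | −1.5 |
| 3 | 75% | 0.2350/0.88 = 26.7% | +1.7 | 35.5% | −0.75 |
| 5 | 50% | 0.2375/0.90 = 26.4% | +1.4 | 33.75% | −2.5 |
| 5 | 75% | 0.2500/0.90 = 27.8% | +2.8 | 35.0% | −1.25 |
| 8 | 50% | 0.2525/0.93 = 27.2% | +2.2 | 32.25% | −4.0 |
| 8 | 75% | 0.2725/0.93 = 29.3% | +4.3 | 34.25% | −2.0 |

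**A second grid.** With mortality (A/B) of 10/6%, 15/10% and 20/12%, base disability 15% to 25% and q 40% to 70%, the survivors-only gap is 0.6 to 5.0 points against Arm B. Death or disability favours Arm B by 1.2 to 4.8 points. With equal mortality of 12% and the same babies surviving, both gaps are zero.

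**Against sampling error.** Survivors number 330·0.85 ≈ 280 in A and 330·0.88 ≈ 290 to 330·0.93 ≈ 307 in B. At s = 8, q = 75%, the standard error of the disability difference is √(0.25·0.75/280 + 0.293·0.707/307) ≈ 3.7 points, so 4.3 points is about 1.2 standard errors. The largest gap in the second grid (15% against 20%, with 264 and 290 survivors) has standard error √(0.15·0.85/264 + 0.20·0.80/290) ≈ 3.2 points, so 5.0 points is about 1.6 standard errors. The composite difference also has a standard error of about 3.7 points.

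**What would cancel it.** If Arm B lowered disability by x among babies who would survive in either arm, the survivors-only gap would vanish at x = s(q − 0.25)/0.85. That is 0.03·0.25/0.85 = 0.9 points at the mild end and 0.08·0.50/0.85 = 4.7 points at the extreme end.

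**The case against.** The strongest reply is that the protocol never states a survivors-only comparison. Sections 1.2 and 9.2.2 name an instrument and a time point, section 7.12 keeps the deaths, and the handling of death could be set in the analysis plan. It stands that nothing forecloses a death-or-disability analysis. But the outcome itself is named in the protocol, and as named it has no place for infants who died.

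Four further objections stand:

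- The opposite signs in the table are built into the model. They follow for any q between the base rate and 100%, so they show that a reversal is possible, not that it is likely.
- The model gives Arm B no developmental benefit from fewer major bleeds, although intraventricular bleeds are part of what the trial hopes to prevent.
- The 8-point end turns the whole designed effect into saved lives. In the earlier observational study, major haemorrhage alone was 13% (section 2.1) and death or major bleed 18% (section 9.3), which leaves roughly 5% who died without a major bleed.
- Early deaths by arm will be visible, because death to day 28 and survival to home are separate secondary outcomes.

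A reader might also infer that the intention-to-treat statement is breached. The documents do not support that. The sentence most naturally means analysis by allocated arm and does not promise a value for every infant.

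Finally, a composite is not the only defensible approach; ranked and principal-stratum analyses exist. That bears on the choice of remedy, not on the gap.

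**Conclusion.** The point holds as a weakness in how one secondary outcome is defined. The two-year outcome omits children who die, in a trial whose primary outcome has death as one of its two components. If mortality differs and the extra survivors are at higher risk of impairment, a survivors-only comparison is biased against the arm with better survival. Under the stated assumptions the distortion is about 1 to 4 points, which is within sampling error at 330 per arm. It disappears if mortality is equal and the same babies survive, and it could be offset by a developmental benefit from fewer bleeds.

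Two stronger readings should be resisted. One is that the trial's long-term conclusion would be reversed: neither the distortion nor the composite gain in these scenarios is large enough to settle the matter either way. The other is that deaths make up half of the primary events: death is one of two components, and the protocol gives no share of events that are deaths. The primary analysis and the sample size of 660 are untouched. I would class this as a cheap improvement.

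**What to change.** In sections 1.2 and 9.2.2, define the two-year outcome as death or moderate/severe disability by the two-year corrected-age assessment. Analyse it by allocated arm with all randomised infants in the denominator, and handle missing follow-up as the analysis plan sets out. Report death to two years and disability among survivors beside it, with the survivors-only figure labelled descriptive. State the moderate/severe cut-off explicitly, since section 7.12 gives three groups but no endpoint threshold.

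One detail of wording: section 7.12 counts deaths for two years from randomisation, while the assessment is timed by corrected age, so the definition should name a single horizon.

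The cost is text in the protocol and analysis plan. Deaths and disability grades are already to be collected, so no new data are needed. The small downside is that the composite mixes death with disability, which is why the components must be shown with it.
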